8. STATISTICAL CONSIDERATION AND DATA ANALYSIS PLAN

8.1 Analysis of baseline characteristics

To determine the demographics and characteristics of the patients in the two arms the following data will be collated:

- Age
- Gender
- BMI
- Smoking status
- Significant comorbidities, including peripheral arterial disease, diabetes, rheumatoid arthritis, heart failure.
- VLU location

Confidential – This document and the information contained herein may not be reproduced, used or disclosed without written permission from Cumbria Partnership NHS Foundation Trust Page | 15

Any differences in distribution will be established with Chi-squared test or ANOVA as indicated.

8.2 Primary outcome statistics

The primary objective for this pilot study is the feasibility of conducting a larger scale randomised controlled trial. The secondary outcome statistics will inform the success of this pilot study and will therefore inform whether a larger scale trial is indicated. This will be based on signs of clinical effectiveness, positive patient feedback on the intervention, positive changes in VLU related quality of life, recruitment to time and target, low attrition rates, minimal data queries and lack of or low number of adverse events. If the effect size of the Steplt pedal is large enough, then this pilot trial may provide a definitive answer concerning its clinical effectiveness.

The following descriptive statistics will be reported on:

- Number of patients screened
- Number of patients eligible/ineligible, and percentage of patients consented into the trial
- Number of patients completed the trial/discontinued (plus reasons if discontinued)

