PREVUE v4, dd 12Dec2018

PREVUE; PlantaR flexion Exercise for Venous Ulcer Evaluation, a multi-centre, controlled, prospective, randomized feasibility trial

Version 4, dd 12 December 2018

Chief Investigator's Statement of Ownership and Content.

I, [name], confirm that this protocol is my work and is owned by me. The protocol conforms with standards outlined in the Declaration of Helsinki 1964.

Name (PRINT):___[name]_____

Signature:

Date: ____12 Decl 2018_____

RESEARCH PROTOCOL SUMMARY

TITLE:	PREVUE; PlantaR flexion Exercise for Venous leg UlcEr, a multi- centre, controlled, prospective, randomized feasibility trial
Short title:	PREVUE
IRAS number	222694
Device description	StepIt plantar flexion rocker pedal device. CE-marked and licensed medical device. To be used in this study for indicated purpose, namely plantar flexion exercise.
Study design	Single centre, controlled, prospective randomized feasibility trial
Primary objective	To assess the feasibility of conducting a full RCT in the future - Participants' compliance to StepIt exercise regime
	 Recruitment and attrition rates, willingness of patients to be randomised, response rates to questionnaires, and degrees of missing data Testing of eligibility criteria and ability/willingness of clinical staff to partake in recruitment of participants Adequacy of duration of follow-up (e.g. in relation to VLU healing)
Secondary objectives	To determine the acceptability and efficacy of the step-it pedal as an adjuvant therapy for VLU at 6 and 12 weeks post-baseline - Healing rate (ulcer size, PUSH score) - Ankle motion range - Patient mobility score - VLU-related quality of life score - VLU-related pain - Patient feedback on use of the device
Patient population	A total of 28 participants, over the age of eighteen, with venous leg ulcers and treated either in hospital or at home by the community nursing team. Participants must have the capacity to provide informed written consent and complete patient reported outcome measures. Participants are recruited from the local community nursing caseload and identified in hospital clinics. - 12 Patient will receive treatment as usual (TaU) - 12 Patients will receive TaU plus StepIt exercise programme intervention

	Randomisation will be stratified for ulcer size, with cut-off PUSH
	score of up to 8, and 9 and above.
Sponsor	Cumbria Partnership NHS Foundation Trust
Manufactures O foundan	Charalle Coreboure A.D.
Manufacturer & funder	StepIt System AB,

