4. STUDY HYPOTHESIS

4.1 Primary objective

To assess the feasibility of conducting a full RCT in the future

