6. SUBJECTS

6.1 Anticipated number of research subjects

Since there is no pilot data to base an *a priori* sample size calculation on, it is difficult to make a calculated prediction on the exact number of patients required for a sufficiently powered trial. The outcome of this present study will inform the power calculation for a larger definitive interventional trial. However, below a summary is given for the power potentially achievable for our suggested feasibility sample size. Since some patients may require surgical intervention or may withdraw, a hypothetical 30% dropout rate is calculated into the sample size (actual attrition rate is a study objective). A 1:1 allocation to the control and intervention group respectively will be applied.

The primary outcome, average percentage decrease in ulcer size is used for sample size calculation. Power calculations for sample size, 80% power and 5% significance, based on a Chi-squared test. A priori power calculations using GPower 3.1 software, result in the following sample size summarized in Table 4.

It must be stressed that this current PREVUE study will first and foremost establish if StepIt exercise is acceptable to staff and patients alike, and therefore it is not certain at this stage whether sufficient participants will be enrolled, if participants will be compliant and if they will be compliant for the 12 weeks treatment period.

Table 4, Sample size calculation

	Percentage patients achieving at least 50% reduction in ulcer size	Percentage patients not achieving 50% reduction in ulcer size		
Arm A (hypothetical)	60%	40%		
Arm B (hypothetical)	30%	70%		
	Power beta of 80%, Alpha p-value of 0.05, Effect size 0.6 Sample size required without any drop-out: 22 samples. Sample size with 30% attrition rate included: 28			
	Total of 28 patients: - 12 Patients to receive treatm - 12 Patient to receive treatment	nent as usual ent as usual plus Steplt exercise		

The CONSORT guidelines require a statement on the number of patients assessed for eligibility (Schulz, Altman & Moher 2010). The number of patients screened but who did not meet the inclusion criteria or who declined to participate will be recorded, as will any patients who are lot to follow-up (Appendix 3).

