9. DATA HANDLING AND MONITORING

Data arising from this study is confidential. Identifiable information can only be accessed by delegated members of the study team. Anyone in the research team who does not have a substantive contract with Cumbria Partnership NHS Trusts will need to apply for a letter of access via the NIHR research passport scheme.

Patient identifiable data will only be used within each respective Trust; pseudo-anonymised data are shared with the wider members of the study team. All identifiable data is stored on password protected NHS computer systems. Anonymised data will be shared and stored using security-enabled systems such as password-protection and encryption of e-mails and files. The requirements of the Data Protection Act and NHS Code of Confidentiality will be followed at all times. All researchers will be fully trained in NHS Confidentiality and GCP. Participants' GP practices will be informed that they are taking part in the study.

All paper data will be held in secure locked environments in the office of the Research & Development department in the Carleton Clinic, Carlisle, Cumbria Partnership. Data released (e.g. by publication) will contain no information that could lead to the identification of an individual participant. Upon completion of the study the site files will be archived for a period of 10 years in line with local archiving policy and procedures. Direct access to anonymised data only will be granted to authorised representatives from the sponsor, host institution and the regulatory authorities to permit trial-related monitoring, audits and inspections.

As this concerns a pilot study, the trial will be monitored by the in-house research team who will convene on a monthly basis. A trial steering committee will not be convened for this trial.

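### Section 8.2 judges feasibility, the primary objective, on seven criteria with no pass marks and no rule for combining them; its one numeric anchor is contradictory, and compliance is left out

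*Protocol*

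**What the plan says.** Section 4.1 gives the primary objective: "To assess the feasibility of conducting a full RCT in the future". Section 8.2 says how it will be judged. It first states that "The secondary outcome statistics will inform the success of this pilot study and will therefore inform whether a larger scale trial is indicated". It then gives the basis in two runs: "This will be based on signs of clinical effectiveness, positive patient feedback on the intervention, positive changes in VLU related quality of life", followed by "recruitment to time and target, low attrition rates, minimal data queries and lack of or low number of adverse events". That makes seven criteria. The section adds that, with a sufficiently large effect, "then this pilot trial may provide a definitive answer concerning its clinical effectiveness"; it does not say how large. It ends with a short list of counts to report: screened, eligible, consented, completed and discontinued.

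The figures elsewhere that could serve as marks are these:

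- **Attrition.** Section 6.1 says "a hypothetical 30% dropout rate is calculated into the sample size (actual attrition rate is a study objective". This is a planning value, not a pass mark.
- **Recruitment.** Table 2 anticipates recruitment from May-17 to Dec-18. The summary says "A total of 28 participants" and section 6.1 repeats 28, but both split it as 12 and 12. The lay summary (section 1) gives 48, as 24 and 24.
- **Compliance.** It comes first in the primary outcome list in 5.5.1, with no definition and no threshold, and is not among the 8.2 criteria.

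Section 6.1.1 says the researcher is not blinded. Section 9 gives monitoring to the in-house team and says "A trial steering committee will not be convened for this trial".

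**The concern.** A feasibility trial may simply estimate rates and leave the decision to others. This protocol goes further: it says what the judgement on success and on a larger trial will rest on. Having done so, it states most of the criteria as adjectives such as 'low', 'minimal' and 'positive'. It does not say whether all, most or any of them must be met, or what a mixed result means.

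The judgement concerns the trial's primary question. If the meaning of 'low' is chosen once the attrition rate is known, two readers can take the same data and reach opposite conclusions, both consistent with the protocol. A later trial could then be supported on retention or recruitment figures that a mark set in advance would have failed, or the reverse. Leaving out compliance adds to this, because a self-administered exercise programme that few patients follow could still satisfy all seven criteria.

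**Working it through.** Section 8.2 states no figure to reproduce, so the check has three parts.

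**1. Is there a mark anywhere?** Sections 4, 5.5, 6.1, 8 and 9 were read against each of the seven criteria. Six have no number. The seventh, recruitment, depends on a date and a target. May-17 to Dec-18 is 8 + 12 = 20 months.

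| Target | Source | Rate needed | If 28 enrol by Dec-18 |
|---|---|---|---|
| 24 | 12 + 12, summary and 6.1 | 24/20 = 1.2 per month | target exceeded by 4 |
| 28 | summary and 6.1 | 28/20 = 1.4 per month | target met |
| 48 | lay summary | 48/20 = 2.4 per month | 48 − 28 = 20 short |

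**2. How much does an unstated mark matter?** Attrition is the example. Let X be the number lost out of n, binomial with true rate p. A mark of c is met when X ≤ k, where k is n × c rounded down, and P(X ≤ k) = Σ C(n,x) pˣ(1−p)ⁿ⁻ˣ for x = 0 to k. The marks of 10%, 20% and 30% are assumptions; only 30% appears in the protocol, as a planning value. For n = 28, the products 2.8, 5.6 and 8.4 give k = 2, 5 and 8.

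| n | True attrition | Mark 10% | Mark 20% | Mark 30% |
|---|---|---|---|---|
| 24 (k = 2, 4, 7) | 20% | 0.115 | 0.460 | 0.911 |
| 28 (k = 2, 5, 8) | 20% | 0.061 | 0.501 | 0.910 |
| 28 (k = 2, 5, 8) | 30% | 0.004 | 0.113 | 0.528 |
| 48 (k = 4, 9, 14) | 20% | 0.025 | 0.500 | 0.956 |

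A single result shows the same thing. If 7 of 28 are lost, the rate is 25.0% (exact 95% interval 10.7% to 44.9%). That is 'low' under a 30% mark and not under a 20% mark.

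**3. What must a numeric rule allow for?** At this size any cut-off is noisy. Stopping at 9 or more lost of 28, just above 0.30 × 28 = 8.4, would trigger with probability 1 − 0.528 = 0.472 when true attrition is exactly the planned 30%. A go mark of 5 or fewer would be met 11% of the time at 30% and 50% at 20%. Compliance is measured in one arm only: 10 of 12 compliant is 83%, with an exact 95% interval of 52% to 98%.

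Effect signals are weaker still. For the protocol's hypothetical 60% versus 30% responders, two-sided 5% power by the normal approximation is Φ[(0.3√n − 1.96√(2 × 0.45 × 0.55)) / √(0.6 × 0.4 + 0.3 × 0.7)], with n per arm. This gives 0.31 at n = 12 and 0.35 at n = 14.

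**The case against.** **The SAP may hold the numbers.** Only the protocol was available, and numeric marks could sit in an SAP. This would be decisive if the protocol were silent. But section 8 is headed as the data analysis plan, states the basis for the judgement itself, and does not refer to another document for the marks. An SAP also could not repair a target that the protocol gives three ways. If an SAP does hold marks, the point shrinks to the target conflict, the absence of compliance and a cross-reference.

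**The wording is softer than a decision rule.** Section 8.2 says the results will inform the judgement, and 6.1 treats attrition as something to estimate. This stands in part: nothing makes a larger trial follow automatically, and an error rate for a false verdict is not strictly defined. But 8.2 also says what the judgement will be based on, and that basis is open.

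**The binomial table is close to a truism.** Any pass probability moves with its mark, and attrition is one criterion of seven. Agreed. The table shows how far one criterion can move; it does not show that the overall conclusion would flip.

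Three stronger readings are tempting, and the protocol does not support them:

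- *The plan can never return 'not feasible', or any result can be called a success.* Ten patients enrolled by Dec-18 would miss 24, 28 and 48 alike. A gross shortfall would show.
- *The unblinded in-house team will make the judgement.* Section 9 covers monitoring and the absence of a steering committee. It does not say who decides whether a larger trial is indicated.
- *Every criterion is only an adjective.* Recruitment does point to a date and a number; its fault is that the number is inconsistent.

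**Conclusion.** The concern holds in limited form. The protocol states the basis for judging its primary objective but gives no pass marks and no combination rule. It ties one criterion to a target stated as 24, 28 or 48, and it omits compliance. Outside extreme results, the same data can support either conclusion.

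For attrition alone, at n = 28 and a true rate of 20%, the chance of meeting the criterion runs from 6% to 91% over assumed marks of 10% to 30%. This rests on those assumed marks and on independent losses with a common rate. It does not measure the chance of a wrong overall conclusion, which cannot be calculated without a combination rule.

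This is worth correcting because it concerns the primary question and costs little. It does not invalidate the rates the trial will report.

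**What to change.** 1. Reconcile the enrolment target across the summary, the lay summary, section 6.1 and Table 4.
2. Replace the adjectives in 8.2 with a go / amend / stop table covering recruitment against that target by Dec-18, attrition, compliance (with a definition of compliant), questionnaire completeness, and completeness of week-12 ulcer size.
3. State how the criteria combine, for example whether all must reach 'go', and who makes the judgement. Say whether patient feedback, data queries and adverse events are banded or descriptive.
4. Let the sponsor set the cut-offs and show their operating characteristics beside them. A stop at 9 or more of 28 lost, for instance, would trigger 47% of the time at the planned 30% attrition, which the sponsor may find too harsh.
5. Report each rate with its 95% confidence interval.
6. Keep effect and quality-of-life signals as descriptive support, given power of about 31% to 35% at 12 to 14 per arm.
7. Fix the cut-offs before outcome data are reviewed, and disclose their date and what recruitment and attrition data were already known.

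The cost is one table and a few sentences, by amendment or in an SAP that 8.2 cites; the target itself must be corrected in the protocol. No patients or visits are added. Compliance can come from the exercise diary already planned. The sponsor commits in advance and may have to report 'amend' or 'stop'. Because this version is dated 12 December 2018 and Table 2 anticipates recruitment ending that month with analysis from January 2019, cut-offs added now may not be fully pre-set for recruitment and attrition. Disclosure limits that weakness but does not remove it.

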1. LAY SUMMARY

Venous leg ulcers (VLUs) are the most common type of leg ulcers, affecting 1-3% of the population over 60 years and this incidence is expected to increase with an aging population. There is some evidence to suggest that specific exercise of the calf muscle through for example plantar flexion movement with resistance — moving the front of the foot up and down, similar to what a drummer does when using the foot pedal of a drum - may improve the calf muscle pump function. The positive effects have been shown at the haemodynamic level; they have shown that at least in the short-term there is better blood flow and endurance if the calf muscle is exercised in this manner.

It is acknowledged that venous return from the lower limbs depends on an efficient calf muscle pump and adequate range of ankle motion. Whilst failure of these systems may contribute to venous leg ulceration, evidence suggests that exercise programmes designed to increase the strength of the calf muscle pump through resistance training is feasible and effective in improving calf muscle pump function and ankle range of motion. As yet there remains considerable uncertainty as to the effects of an exercise programme on ulcer healing. There is very limited research data available on the medium- to long-term effects of calf muscle exercising by VLU patients on the healing rate of the ulcer.

This study is a prospective, controlled, randomised, feasibility trial to determine if the use of a CE-approved plantar flexion pedal, developed by StepIt Ltd, will be of benefit to people with VLU in terms of healing rate of VLUs. This pilot aims to assess the feasibility of conducting a full randomised clinical trial in the future. Of the total of 48 patients to be recruited, 24 patients will be randomised to treatment as usual, standard compression therapy only, and the other 24 will be allocated to treatment as usual plus a StepIt exercise programme for 12 weeks. The main outcome measure will be the degree of healing of the VLU. Other outcomes measures will include acceptability of the device training, trial completion rates, and ankle range of motion. Patients with VLUs are less mobile than their aged matched population for a variety of reasons. Initiating foot and ankle exercises may be a first step in increasing physical activity for this population and improving calf muscle pump function.

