There is evidence that exercise of specifically the calf muscle can improve physiological functioning of said muscle. Exercises such as heel raises, flexion, extension and rotation of the ankles have been shown to increase venous return (Padberg, Johnston & Sisto, 2004, Roaldsen *et al* 2006, Jull *et al* 2009) and clinical guidelines recommend ankle exercises and walking (RCN 1998, SIGN 2010). There is paucity of studies demonstrating any correlation with exercise and improvement in ulcer healing but the suggestion that exercise as an adjunct therapy may improve the time to VLU healing warrants exploration.

Patients with venous leg ulcers report multiple co-morbidities and are more likely to be sedentary than age matched controls (Persoon *et al* 2004, Roaldsen *et al* 2006). Whilst exercise could be of particular benefit for this group of patients' research suggests that around 50% of sedentary adults who start an exercise programme stop within the first 6 months of involvement (Heinen *et al* 2007). This study will apply a step—it rocker pedal for the first time in patients with VLU's in addition to the standard treatment of compression therapy. This is a small pedal device that can be used from a seated position and was first devised to help alleviate the risk of deep vein thrombosis for travellers on long haul flights. Patients may be receptive to this form of exercise especially if they are elderly, frail, have limited mobility, have a fear of falling or are housebound.

The aim of this initial randomised, controlled, prospective feasibility study is to determine the acceptability and efficacy of the step-it pedal as an adjuvant therapy for VLU with a primary outcome measure of VLU healing. This is a pilot aiming to assess the feasibility of conducting a full randomised clinical trial in the future.

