5.5 Outcome measures

5.5.1 **Primary outcome measures**

To assess the feasibility of conducting a full CRT in the future, the primary outcome measures are mainly:

Trial-related outcome measures

- Participants' compliance to StepIt exercise regime
- Recruitment and attrition rates, willingness of patients to be randomised, response rates to questionnaires, and degrees of missing data
- Testing of eligibility criteria and ability/willingness of clinical staff to partake in recruitment of participants
- Ability of sites and clinicians to recruit and randomise patients, irrespective of care setting
- To assess any training requirements
- Adequacy of duration of follow-up (e.g. in relation to VLU healing)
- Fitness for purpose of data collection methods including across and between care settings
- Adverse events

5.5.2 **Secondary outcome measures**

The primary outcome for this pilot trial will be the feasibility of conducting a full CRT in the future. However, this study also aims to provide preliminary results regarding the acceptability and efficacy of a simple StepIt pedal as an adjuvant therapy for on VLU healing.

Clinical outcome measures

• VLU size, measured with Convatec grid tool (outcome measure used for calculating potential power of this present study)

Confidential – This document and the information contained herein may not be reproduced, used or disclosed without written permission from Cumbria Partnership NHS Foundation Trust Page | 11

- Size and characteristics of VLU, determined with PUSH score
- Mobility score
- Ankle range of motion
- Pain score
- Quality of life score, determined with Charing Cross Venous Ulcer Questionnaire
- Exercise diary
- Participant opinion on trial participation
- Patient withdrawal rates due to change in management (e.g. need for surgery)
- VLU infection rates

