6.1.1 Randomisation

Following written consent patients will be allocated at random to the control or intervention group, using a non-restricted randomised sequence generated for the whole sample using a free ware randomisation programme, see https://www.randomizer.org/. The randomisation will be stratified for VLU size, with one group being those with a PUSH score of 8 or lower and the other with a PUSH score of 9 or higher. Sequential envelopes with each next randomisation allocation will be used to achieve concealment. It is recognised that random selection does not guarantee representativeness but variables which may affect the outcome variable are more likely to be balanced out and reliability enhanced (Thomas 1990).

As the study involves a self-administered intervention of necessity it is not possible to achieve blinding for the participants. Due to the pilot nature of this study, the researcher will not be blinded either to the subjects intervention, although this can be considered as part of a larger trial since it would further reduce any risk of bias. However, the primary outcome measure, size of the VLU is a quantitative outcome measure which is less prone to bias than for example a patient reported outcome measure or a clinician reported outcome measure.

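### The protocol gives conflicting primary outcomes and says a small unblinded pilot may settle effectiveness; the design supports feasibility conclusions only

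*Protocol*

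**What the plan says.** **Feasibility is primary in some places.** Section 4.1 gives it as the primary objective. Section 5.5.2 states "The primary outcome for this pilot trial will be the feasibility of conducting a full CRT in the future" and lists ulcer size among the secondary measures. Section 8.2 opens with "The primary objective for this pilot study is the feasibility of conducting a larger scale randomised controlled trial".

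**Ulcer healing or size is main or primary in others.** The lay summary says "The main outcome measure will be the degree of healing of the VLU". The introduction describes the study "with a primary outcome measure of VLU healing". Section 6.1 bases the sample size on ulcer-size reduction and calls it the primary outcome. Section 6.1.1, on blinding, refers to "the primary outcome measure, size of the VLU is a quantitative outcome measure".

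**Section 8.2 ties the pilot's success to efficacy.** It says "The secondary outcome statistics will inform the success of this pilot study and will therefore inform whether a larger scale trial is indicated", and continues "This will be based on signs of clinical effectiveness, positive patient feedback on the intervention, positive changes in VLU related quality of life", followed by recruitment, attrition, data queries and adverse events. It then says that, given a sufficiently large effect, "then this pilot trial may provide a definitive answer concerning its clinical effectiveness". No size of effect is given.

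**Section 6.1 points the other way.** It says there are no pilot data for a sample size calculation and that the results will feed the power calculation of a larger, definitive trial.

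**The concern.** A protocol should have one answer to the question of what the trial is for. Here the answer depends on the section read, and an analysis plan written later cannot tell which one the protocol intends.

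The claim in section 8.2 raises the stakes. If a favourable ulcer-size result may be called definitive, or may steer the decision on a larger trial, that decision rests on the weakest part of the design. Two errors become likely: dropping a useful device because a small trial showed little, and carrying an inflated effect into the next sample size calculation.

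**Working it through.** **Inputs.** Section 6.1 and Table 4: 60% v 30% of patients with at least a 50% reduction in ulcer size, chi-squared test, 5% significance, 80% power, effect size 0.6, 22 patients without drop-out, 28 with 30% attrition, 1:1 allocation. The planned total is not consistent: 28 in the summary and Table 4, 12 + 12 by arm in the same two places, and 48 (24 + 24) in the lay summary. A range is therefore shown.

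**The plan's own figure.** For a 1-df chi-squared test with w = 0.6 and N = 22, the noncentrality is 22 × 0.36 = 7.92 and power is 80.4%. So 22 reproduces. The 28 matches 22 × 1.3 = 28.6 rounded down (22/0.7 gives 32).

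**Does 0.6 describe 60% v 30% in two arms?** For two equal arms w = 0.30 / (2 × √(0.45 × 0.55)) = 0.302, which needs N = 87. The usual two-proportion formula gives

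n per arm = [1.96 × √(2 × 0.45 × 0.55) + 0.842 × √(0.24 + 0.21)]² / 0.30² = 42,

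that is 84 evaluable, or 84/0.7 = 120 randomised. The apparent 80% power at 22 patients does not apply to the protocol's own scenario.

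**Exact behaviour under 60% v 30%.** All pairs of binomial counts (x, y) were enumerated. A pair is significant when (x/n − y/n)² / [p̄(1 − p̄) × 2/n] exceeds 3.84, where p̄ = (x + y)/2n (uncorrected Pearson, p < 0.05). The mean gap is the average absolute difference among significant results.

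| Evaluable per arm | Basis | Power | Mean significant gap | Ratio to 30 points |
|---|---|---|---|---|
| 10 | 28 less 30% (19.6) | 25% | 57 points | 1.9 |
| 14 | 28, no loss | 33% | 49 points | 1.6 |
| 24 | 48, no loss | 59% | 39 points | 1.3 |

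At 10 per arm no gap below 40 points can be significant. For 3 v 0 the statistic is 0.09 / (0.15 × 0.85 × 0.2) = 3.53, which falls short; for 4 v 0 it is 0.16 / (0.2 × 0.8 × 0.2) = 5.0.

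**A much larger true effect.** With 90% v 30% and 10 per arm, power is 82% and the mean significant gap is 66 points against a true 60, a ratio of 1.1.

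**Number of comparisons.** Section 8.3 compares the groups on six outcomes. Ulcer size, PUSH score and pain are assessed between six-weekly time points, so two intervals each; mobility, ankle motion and quality of life are first v last visit. That is at most 3 × 2 + 3 = 9 group comparisons. Under independence the chance of at least one false positive at 5% is 1 − 0.95⁶ = 26% for six and 1 − 0.95⁹ = 37% for nine. Both are upper-end figures, because the outcomes are correlated; surface area, for instance, is a PUSH sub-score (Appendix 1).

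**Blinding.** Section 6.1.1 leaves participants and researcher unblinded. Under section 5.4 the community nurse measures the ulcer, and no blinding of that measurement is described.

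**The case against.** The strongest defence is that the wording of section 8.2 is mild. The effectiveness sentence is conditional, efficacy is one of seven considerations, the verb is to inform, and section 6.1 already cautions about power. Section 6.1.1 adds that a measured ulcer size is less open to bias than a reported outcome. All of this is fair and limits the point. It does not rescue the sentence: the triggering effect is never quantified, and a quantitative measure taken without blinding can still be biased.

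Several stronger readings are tempting and are not supported:

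- **That efficacy decides progression, or does so through a significance test.** Section 8.2 does not say this, and signs of effectiveness are nowhere defined as p < 0.05. The averages over significant results illustrate a risk; they do not model a stated rule.
- **That any significant result must be exaggerated.** Under 60% v 30% this is strictly so at 10 per arm. At 14 per arm a 29-point gap can be significant at the extremes, and at 24 per arm about 20% of significant results show 30 points or less. With a very large true effect the inflation is slight.
- **That no lead clinical outcome is designated.** Ulcer size is designated in sections 6.1 and 6.1.1, and section 5.5.2 marks it as the basis for power. The fault is conflicting designation.
- **That twelve tests are planned.** Section 8.3 supports nine at most.

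The power figures also use the responder chi-squared test from section 6.1, whereas section 8.3 plans a Mann-Whitney test on ulcer-size change. They describe the sizing scenario and not the planned analysis.

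**Conclusion.** The point holds in this form. The protocol contradicts itself on its primary outcome, and the possibility of a definitive answer raised in section 8.2 conflicts with section 6.1 and with a small, unblinded design.

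On the protocol's own scenario, power is 25% to 33% for a total of 28, with and without the assumed attrition, and 59% for the 48 in the lay summary before any loss. Average overstatement among significant results runs from 1.9 down to 1.3 times. These figures assume a true 60% v 30%, the uncorrected Pearson test and equal arms. The false-positive figures of 26% and 37% assume independence and so are upper-end values.

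The consequence is that an efficacy-based decision on the next trial could mislead. A reader might infer that it would necessarily be wrong; the documents do not show that. This should be changed, but it is a matter of wording and of what may be concluded, and does not invalidate the feasibility study.

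**What to change.** 1. Delete the sentence in section 8.2 that allows a definitive conclusion on effectiveness.
2. Name feasibility as the only primary outcome in the lay summary, the introduction and sections 6.1 and 6.1.1. Call ulcer size the lead secondary clinical outcome.
3. In section 8.2, base the progression decision on feasibility measures the protocol already lists: recruitment, retention, adherence and data completeness, each with a 95% confidence interval.
4. Report efficacy as estimates with 95% confidence intervals. Do not use its significance or observed size alone to decide on, or to size, the next trial.
5. If progression thresholds are added, state when they were set. This version is dated 12 December 2018 and Table 2 ends recruitment in December 2018, so a threshold introduced after recruitment has largely finished should be labelled as such.

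**Cost.** A protocol amendment with the review-body approval described in section 10.1. No patient, visit or measurement is added. The sponsor gives up a claim that the design cannot support.
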